### Safety Outcomes

- (i) symptomatic intracranial hemorrhage
- (ii) major bleeding due to femoral artery access complications including groin hematoma, retroperitoneal hematoma [definition]
- (iii) contrast nephropathy
- (iv) total radiation dose (CT, CTA, angiography)
- (v) malignant MCA infarction
- (vi) hemicraniectomy

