### Process and Quality Outcomes

- (i) CT-to-groin puncture time (“Picture-to-puncture”)
- (ii) CT-to-recanalization time
- (iii) Aspiration pneumonia
- (iv) Rate of use of general anesthesia
- (v) Rate of symptomatic deep venous thrombosis / pulmonary embolism
- (vi) Proportion of patients with any SAE per site
- (vii) Qualitative Interview to assess the process of waiver/deferral of consent.

Symptomatic intracranial hemorrhage defined as new intracranial hemorrhage (ICH, SAH, IVH, SDH) associated with clinical evidence of neurological worsening, in which, the hemorrhage is judged to be the most important cause of the neurological worsening. Clinical worsening will be guided by the NIHSS score of a minimum of 2 or more points different from baseline.

Major extracranial hemorrhage defined as life threatening, resulting in hemodynamic compromise or hypovolemic shock, requiring inotropic support or other means to maintain cardiac output, requiring blood transfusion of more than 2 units of packed red blood cells, or associated with a fall in hemoglobin greater than or equal to 5 g/L.

Contrast nephropathy will be defined as any rise of the serum creatinine by 50% or more between the baseline pre-treatment level and that measured at 24h post-treatment.

Total radiation dose will be measured in mSv and recorded directly from the CT scanner. Dose-length product will be recorded directly from the CT scanner.

Malignant MCA infarction will be defined as any large infarction with mass effect observed on imaging where treatment (medical or surgical) is required for the treatment of mass effect.

Hemicraniectomy will be defined as that surgical procedure used to decompress the swollen hemisphere.

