### Study Enrolment Process

Patients will be identified using usual standard of care screening methods at the acute stroke hospital. This will include screening by neurology residents, fellows, nurse practitioners, physician assistants or faculty physicians. Sites will only be selected to participate in the study if they have intact mechanisms for screening this population of patients. This includes standard of care use of CT angiography among stroke patients. All patients will undergo an acute clinical assessment, blood laboratory assessment and baseline brain imaging with acute CT and CTA. CT perfusion or MR imaging are not mandated in the study, but not prohibited. However from the perspective of imaging to recanalization time, the first slice of the baseline non-contrast CT is when the clock starts. It is mandated that a CT perfusion cannot be performed before the CTA.

If the patient remains eligible after completion of routine screening, the patient will be consented (as required) and enrolled into the study. The patient is considered enrolled into the study once the randomization assignment has been received (eg. study number assigned over the internet). A patient who consents but is not randomized will be considered a screen failure.

Treatment will be assigned using 1:1 randomization. Randomization will be conducted using a web-based algorithm with treatment assignment allocated by web-based real-time interaction with the site. The initial randomization of the first 40 patients will be completed using randomly ordered permuted blocks of 4 or 6 and assigned by site. Thereafter randomization, subject data will be entered into an on-line database within 6 hours of patient enrolment. A minimal sufficient balance method will be used to ensure that the patients entered into the trial will be matched between control and active treatment arms on the key variables of site, age, sex, baseline NIHSS score, baseline NCCT ASPECTS score, and location of the symptomatic target arterial occlusive lesion. This method will ensure that by the end of the trial, the patients are well matched for important prognostic variables and therefore that by chance, the groups are not unbalanced on one particular variable.

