| EQ-5D  |          |       |                                       |                                       |                              | X                | X                 |
| NCCT head  | X        |       | X*                                    |                                       |                              |                  |                   |
| CTA COW  | X        | X**   |                                       |                                       |                              |                  |                   |
| Full emergency stroke labs                         | X‡       |       |                                       |                                       |                              |                  |                   |
| Creatinine and CBC only                            |          |       | X                                     |                                       |                              |                  |                   |
| ECG  | X‡       |       | X                                     |                                       |                              |                  |                   |
| Adverse event assessment                           |          | X     | X                                     | X                                     | X                            | X                | X                 |
| Prior medications                                  | X‡       |       |                                       |                                       |                              |                  |                   |
| Concomitant medications                            | X        | X     | X                                     | X                                     | X                            | X                |                   |
| Consent process survey                             |          |       | X                                     |                                       |                              |                  | X                 |

\*Day +1 NCCT head may be supplanted by an MR head at the discretion of the local site. We encourage this.

\*\*2-8 hours CTA COW – Control group only. We encourage early CTA within this time window. If there is a situation that arises where a subject randomized to the endovascular group does not have a final cerebral angiogram performed, that patient should have a 2-8h CTA to evaluate recanalization.

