### **Evaluations Following Randomization**

Creatinine and CBC are collected at 24 ( $\pm$  6 hours). An ECG will be completed at 24 ( $\pm$  6 hours). Subjects randomized to the control arm (best medical management) will have a CTA COW completed at 2-8 hours following randomization. If there is a situation that arises where a subject randomized to the endovascular group does not have a final cerebral angiogram performed, that patient should have a 2-8h CTA to evaluate recanalization. All subjects will undergo a follow-up NCCT scan or brain MRI (including a minimum of diffusion-weighted imaging [DWI], gradient-echo [GRE], FLAIR, and intracranial MR angiography [MRA]) at 24 hours ( $\pm$  6 hours) from the time of randomization. All subjects will have an historical mRS and miFUNCTION scale scores evaluated at 24 hours, 30 days ( $\pm$  7 days) and 90 days ( $\pm$  7 days). All subjects also undergo a NIHSS assessment at 2-8h (at the time of CTA), 24 hours ( $\pm$  6 hours), 48 hours ( $\pm$  6 hours), and 5 days or discharge, whichever comes first, 30 days ( $\pm$  5 days) and 90 days ( $\pm$  7 days). Where the deferral of consent process is approved and in use, all subjects who are enrolled using this process should have the deferral of consent survey completed in the 1-5d window and at 90 days. A mRS will be completed at 30 days ( $\pm$  5 days) and 90 days ( $\pm$  7 days). The Barthel Index will be completed at 30 days ( $\pm$  5 days) and 90 days ( $\pm$  7 days). The EQ-5D will be completed at 30 days ( $\pm$  5 days) and 90 days ( $\pm$  7 days). A cognitive battery using the following subscales will be completed at 90 days ( $\pm$  7 days): Trailmaking A & B, MoCA, Boston Naming test and Sunnybrook hemi-neglect battery. At minimum 90-day outcomes assessments on the mRS, NIHSS and BI should be conducted by an evaluator blind to the acute treatment. It is preferred if all 90-day outcome assessments are conducted by a blinded evaluator.

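### The protocol defines total radiation dose as CT, CTA and angiography, but the only source it names for that total is the CT scanner, so the rule read literally leaves out the endovascular procedure

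*Protocol*

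**What the plan says.** Item (iv) of the Protocol's Safety Outcomes is "total radiation dose (CT, CTA, angiography" (closing bracket follows). CTA has its own place in that list, so angiography there means the catheter procedure.

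The definitions printed under Process and Quality Outcomes state how the figure is obtained: "Total radiation dose will be measured in mSv and recorded directly from the CT scanner". The next sentence adds a second quantity from the same machine: "Dose-length product will be recorded directly from the CT scanner". Neither sentence mentions the angiography unit, and no other section of the Protocol gives a source, quantity or unit for the angiography dose.

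Three statements in the follow-up plan decide which exposures a CT scanner would see in each arm:

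- Evaluations Following Randomization: "Subjects randomized to the control arm (best medical management) will have a CTA COW completed at 2-8 hours following randomization". The footnote to the Schedule of Assessments agrees: "2-8 hours CTA COW – Control group only".
- Both places make one exception. If an endovascular patient has no final cerebral angiogram, "that patient should have a 2-8h CTA to evaluate recanalization".
- The 24-hour imaging rule is the same in both arms: "All subjects will undergo a follow-up NCCT scan or brain MRI".

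**The concern.** The outcome and its measurement rule do not match. The outcome has three components, and the rule names a source that can supply two of them. The missing component is not spread evenly over the trial: it is the radiation delivered by the experimental treatment itself. The scheduled CT exposures are also uneven, but in the other direction, because the 2-8 hour CTA belongs by default to the control arm.

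At stake is the between-arm comparison of a listed safety outcome. Safety of the endovascular approach is a stated secondary objective in the synopsis. The Protocol itself treats radiation as relevant: Appendix 1 gives dose as a reason to avoid CT perfusion. A total that cannot register the procedure says nothing about what the intervention adds. This is also a data-capture matter. If the dose is not transcribed around the time of the procedure, a later analysis plan may be unable to recover it.

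**Working it through.** The Protocol states no dose, power or threshold for this outcome, so there is no figure to reproduce. The check is a count of scheduled exposures per patient, split by whether a CT scanner records them.

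**Inputs**

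- Baseline non-contrast CT and CTA: both arms (Schedule of Assessments).
- 2-8 hour CTA: all controls, and a share f of endovascular patients, namely those without a final angiogram (Schedule of Assessments footnote; Evaluations Following Randomization). The documents do not give f.
- 24-hour non-contrast CT or MR: same rule in both arms (same sections).
- Catheter angiography: endovascular arm, in the angiography suite.
- Allocation: "Treatment will be assigned using 1:1 randomization" (Study Enrolment Process).

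**Count of scheduled exposures**

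| Exposure | Control | Endovascular | Seen by CT scanner |
|---|---|---|---|
| Baseline non-contrast CT | 1 | 1 | yes |
| Baseline CTA | 1 | 1 | yes |
| 2-8 h CTA | 1 | f | yes |
| 24 h non-contrast CT (0 if MR) | 1 | 1 | yes |
| Catheter procedure | 0 | 1 | no |
| **CT-scanner total** | **4** | **3 + f** | |
| **CT-scanner total if MR at 24 h** | **3** | **2 + f** | |

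Control minus endovascular, CT scanner only: 4 - (3 + f) = 1 - f CTAs per patient. With MR at 24 hours: 3 - (2 + f) = 1 - f, the same. For assumed values of f:

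- f = 0: 1 CTA
- f = 0.1: 0.9 CTA
- f = 0.2: 0.8 CTA

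The difference is positive for every f below 1.

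**From counts to dose**

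Let A be the dose of one 2-8 hour CTA, P the mean procedural dose per patient randomised to endovascular treatment, and U the between-arm difference (endovascular minus control) in all other CT exposure, such as CT perfusion, unscheduled safety scans, or unequal use of MR at 24 hours. For endovascular minus control:

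- Recorded under the literal rule: U - (1 - f)A
- Total as listed in Safety Outcomes: P + U - (1 - f)A
- Recorded minus total: -P

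Two results follow. First, P does not appear in the recorded difference, so that difference is the same whatever the procedure delivers. Second, the error is -P whatever A, f and U are. It always lowers the endovascular arm relative to control. If some controls crossed over to a procedure, P becomes the difference between the arms in mean procedural dose. The conclusion holds as long as that is positive.

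**What cannot be computed**

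With U = 0, the true difference is P - (1 - f)A. It is positive only if P exceeds (1 - f)A. Neither P nor A is given in the documents, so neither the size nor the sign can be stated.

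**The case against.** The strongest reply is that the definition does not exclude other sources. It names the CT scanner without saying that nothing else counts, and the outcome list shows that angiography was meant to be included. On this view a site reading both places finds a missing source, not an instruction to leave the procedure out. The case report form and the Manual of Procedures, which are not shown, may already hold an angiography dose field. This stands in part. It means the dose may not in fact be lost, and the finding has to be conditional on a literal reading. It does not remove the mismatch: the sentence speaks of the total, assigns that total to the CT scanner, and is followed by a second quantity from the same machine.

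A reader might go further and infer three things that the documents do not support:

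- **That the comparison would point the wrong way.** This needs the procedural dose to exceed (1 - f) times the dose of one CTA. The documents give neither dose.
- **That controls would certainly look more irradiated, by exactly one CTA each.** The figure is (1 - f), and it holds only if other CT use is equal. MR may replace CT at 24 hours, CT perfusion is permitted, and extra safety scans are foreseen under Imaging. Any imbalance in these would move the recorded difference.
- **That the procedural dose of about 250 patients is recorded as zero.** The figure of 250 is half the maximum of 500 in Statistical Considerations. Half of the 400 patients on which the trial is powered is 200. Whether the dose goes unrecorded depends on forms that are not shown.

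It is also fair to say that the consequence is limited. Radiation dose has no hypothesis, threshold or stopping rule, it is absent from the synopsis list of safety events, and the primary analysis does not use it.

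**Conclusion.** The point holds as an inconsistency between a listed safety outcome and its stated measurement rule. Taken literally, the rule omits the endovascular arm's procedural exposure. The recorded difference is then biased in favour of that arm by P, its mean procedural dose, and carries no information about P. On scheduled imaging alone, with other CT use equal, controls also show (1 - f) more recorded CTAs per patient, for example 0.8 to 1 for f between 0.2 and 0.

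This rests on three assumptions: the definition is followed as written, no form outside the Protocol already captures the angiography dose, and few controls cross over to a procedure. The true between-arm difference, including its sign, is not determinable from the documents. The correction should be made because the comparison cannot be validly reported as a total under the present wording. The primary outcome is not affected.

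**What to change.** Reconcile item (iv) of Safety Outcomes with the definition under Process and Quality Outcomes. Either of two changes is enough:

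1. Keep the outcome as a total. State that the CT and CTA components come from the CT scanner, that the angiography component comes from the angiography unit's dose report, and that they are combined on a common scale by a conversion stated in advance.
2. Rename the outcome CT radiation dose, matching the source now named, and report the procedural dose as a separate item.

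Under either version it would help to show the 2-8 hour CTA as its own component, since the study itself schedules it mainly in one arm. That is a presentational preference and is not needed to remove the inconsistency.

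The cost is a wording change and one field transcribed from the angiography dose report, or the wording change alone if that field already exists. No treatment or imaging schedule changes.

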## Selection and Enrolment of Subjects

### Inclusion Criteria

#### Clinical (Heterogeneous sampling frame)

1. Acute ischemic stroke
2. Age 18 or greater
3. Onset (last-seen-well) time to randomization time < 12 hours.
4. Disabling stroke defined as a baseline NIHSS > 5 at the time of randomization.
5. Pre-stroke (24 hours prior to stroke onset) independent functional status in activities of daily living with modified Barthel Index > 90. Patient must be living in their own home, apartment or seniors lodge where no nursing care is required.

#### Imaging (Homogeneous target population)

6. Confirmed symptomatic intracranial occlusion, based on single phase, multiphase or dynamic CTA, at one or more of the following locations: Carotid T/L, M1 MCA, or M1-MCA equivalent (2 or more M2-MCAs). Anterior temporal artery is not considered an M2.
7. Non-contrast CT and CTA for trial eligibility performed or repeated at ESCAPE stroke center with endovascular suite on-site.
8. Endovascular treatment intended to be initiated (groin puncture) within 60 minutes of baseline non-contrast CT with target baseline non-contrast CT to first recanalization of 90 minutes.
9. Signed informed consent or appropriate signed deferral of consent where approved.

### Exclusion Criteria

1. Baseline non-contrast CT reveals a moderate/large core defined as extensive early ischemic changes of ASPECTS 0-5 in the territory of symptomatic intracranial occlusion.
2. Other confirmation of a moderate to large core defined one of three ways:
  - a. *On a single phase, multiphase or dynamic CTA*: no or minimal collaterals in a region greater than 50% of the MCA territory when compared to pial filling on the contralateral side (multiphase/dynamic CTA preferred)  
OR
  - b. *On CT perfusion* ( $\geq 8$  cm coverage): a low CBV and very low CBF ASPECTS <6 AND in the symptomatic MCA territory  
OR

- c. *On CT perfusion (<8 cm coverage): a region of low CBV and very low CBF >1/3 of the CTP imaged symptomatic MCA territory.*
3. Groin puncture is not possible within 60 minutes of the first slice of non-contrast CT acquisition (please note that if CTP is performed it should be done after CTA).
4. No femoral pulses or very difficult endovascular access that will result in a non-contrast CT-to-recanalization time that is longer than 90 minutes, or will result in an inability to deliver endovascular therapy.
5. Pregnancy; if a woman is of child-bearing potential a urine or serum beta HCG test is positive.
6. Severe contrast allergy or absolute contraindication to iodinated contrast.
7. Suspected intracranial dissection as a cause of stroke.
8. Clinical history, past imaging or clinical judgment suggests that the intracranial occlusion is chronic.
9. Patient has a severe or fatal comorbid illness that will prevent improvement or follow-up or that will render the procedure unlikely to benefit the patient.

*This population is expected to consist of patients:*

1. *with unknown time of stroke onset but less than 12 hour time of last known normal.*
2. *stroke-on-awakening but less than 12 hours from going to bed.*
3. *stroke with time of onset <4.5h but stroke patients with an elevated INR > 1.7 precluding routine thrombolysis*
4. *stroke with time of onset <4.5h but taking anticoagulants (dabigatran, apixaban, rivaroxaban, LMWH, vitamin K antagonists and others),*
5. *stroke with time of onset <4.5h but recent MI, surgery, or bleeding prohibiting standard of care thrombolysis*
6. *stroke patients who have received intravenous tPA in a drip-and-ship paradigm and fulfill inclusion/exclusion criteria after repeat clinical and imaging evaluation at the ESCAPE site*
7. *stroke patients who have received intravenous tPA at the ESCAPE site <4.5h and can be rapidly moved to the neuro-angiography suite in a direct IV-IA approach. In this case, the patient meets all the ESCAPE inclusion/criteria and is additionally treated with IV tPA.*
8. *In-hospital stroke patients who meet all other criteria, and in particular that they had a functional status (Barthel Index > 90) immediately prior to the stroke. [For example: severely ill hospitalized patients are not candidates for the study; patients with stroke due to elective coronary angiography are potentially eligible for inclusion.]*

*The study population will be clinically heterogeneous, but will be highly homogenous as defined by imaging. Thus the selection of patients will have a clinical component to define the sample frame and a second imaging component to refine the population.*

### Study Enrolment Process

Patients will be identified using usual standard of care screening methods at the acute stroke hospital. This will include screening by neurology residents, fellows, nurse practitioners, physician assistants or faculty physicians. Sites will only be selected to participate in the study if they have intact mechanisms for screening this population of patients. This includes standard of care use of CT angiography among stroke patients. All patients will undergo an acute clinical assessment, blood laboratory assessment and baseline brain imaging with acute CT and CTA. CT perfusion or MR imaging are not mandated in the study, but not prohibited. However from the perspective of imaging to recanalization time, the first slice of the baseline non-contrast CT is when the clock starts. It is mandated that a CT perfusion cannot be performed before the CTA.

If the patient remains eligible after completion of routine screening, the patient will be consented (as required) and enrolled into the study. The patient is considered enrolled into the study once the randomization assignment has been received (eg. study number assigned over the internet). A patient who consents but is not randomized will be considered a screen failure.

Treatment will be assigned using 1:1 randomization. Randomization will be conducted using a web-based algorithm with treatment assignment allocated by web-based real-time interaction with the site. The initial randomization of the first 40 patients will be completed using randomly ordered permuted blocks of 4 or 6 and assigned by site. Thereafter randomization, subject data will be entered into an on-line database within 6 hours of patient enrolment. A minimal sufficient balance method will be used to ensure that the patients entered into the trial will be matched between control and active treatment arms on the key variables of site, age, sex, baseline NIHSS score, baseline NCCT ASPECTS score, and location of the symptomatic target arterial occlusive lesion. This method will ensure that by the end of the trial, the patients are well matched for important prognostic variables and therefore that by chance, the groups are not unbalanced on one particular variable.

